### Global Longitudinal Stain (GLS)

Advanced echocardiographic techniques such as GLS have evolved for direct assessment of the myocardial function. This technique may be beneficial for the assessment of sepsisinduced cardiomyopathy [1,2,3,4,5]. It is different from 2D or 3D LVEF in that it allows more regions of the LV cavity to be assessed simultaneously via myocyte deformation, as compared to volumetric measurement of LV cavity function. Although the modalities of scanning are all assessing cardiac function, the processes by which they measure function differ.

With the use of advanced techniques, septic-induced cardiomyopathy may be commonly diagnosed. It may help identify patients who are critically ill from sepsis and target treatment accordingly. The current management pathways for patients with reduced EF would include follow-up with specialist heart failure input alongside treatment optimization with pharmacotherapy. If patients are found to have cardiac dysfunction early (as evidenced by reduced GLS or EF) then they could be referred on for specialist assessment and treatment early. The current management pathways for patients with reduced EF would include follow-up with specialist heart failure input alongside treatment optimization early (as evidenced by reduced GLS or EF) then they could be referred on for specialist assessment and treatment early. The current management pathways for patients with reduced EF would include follow-up with specialist heart failure input alongside treatment optimization with pharmacotherapy.

The long-term effects of septic cardiomyopathy have not been studied with regards to heart failure. A single study has observed that only one-third of patients survive post septic shock or sepsis, and advanced echocardiographic imaging was not performed on any of the participants [27].

#### Biomarkers

Highly sensitive biomarkers have established roles in the detection of myocardial damage in the context of ischemia and strain. The new high-sensitivity troponin assays may allow clinicians to better stratify risk in other potentially high-risk populations [7]. However, the utility of troponin testing in septic cardiomyopathy is unclear and awaits further investigation [7]. Raised levels of high-sensitivity troponin were independently associated with an increased risk for thrombotic and vascular events as well as cardiovascular death[7,8]. This study looks to explore any association of high sensitivity troponin with reduced GLS.

Guidelines from the American College of Cardiology Foundation (ACCF) and the American Heart Association (AHA) list as a class I recommendation the use of BNP or NT-proBNP values in the diagnosis and prognostication of heart failure [9]. Increased or persistent elevation in natriuretic peptide levels is a poor prognostic factor [10]. As a marker of LV dysfunction, natriuretic peptides are not helpful in diagnosing myocardial ischemia and acute coronary syndrome (ACS) [11]. However, B-type natriuretic peptide BNP and NT-proBNP levels may be useful for risk stratification in patients with acute coronary syndrome (ACS),

and they may predict clinical chronic heart failure. A multi-marker approach may improve risk stratification following myocardial injury [10,11]. There is an emerging role for natriuretic peptide biomarkers in population screening to detect incident HF [12,13,14]. Elevated plasma levels of natriuretic peptide biomarkers are associated with a wide variety of cardiac and non-cardiac causes [15,16]. Like natriuretic peptides, cardiac troponin levels may be of prognostic value in the setting of chronic or acute decompensated Heart Failure HF, but are more sensitive for myocyte injury or necrosis [17].

It is recognised that strategies that combine multiple biomarkers may be beneficial in guiding cardiac therapies in the future [18,19].

## 5.0 PRELIMINARY STUDIES AND EXPERIENCE OF INVESTIGATORS

#### Investigator Team

The investigators are clinically active members at Queen Alexandra Hospital, Portsmouth. The research team is ideally placed to deliver this study combining the expertise with Intensive Care Unit ICU and the Cardiology department. Whilst some members of the research team have limited research experience, they will be supported and mentored appropriately and all staff are GCP trained. There are no additional clinical training requirements for the study team.

The team is well supported by the Critical Care department which is frequently involved in large multicentre clinical trials.

## **Preliminary Studies**

Previous audit and service evaluation have been performed in 2017 for submission as abstracts to Intensive Care Society (ICS) and British Society of Echocardiography (BSE) looking at feasibility of performing the novel echo techniques and to identify a subset of patients who may show normal EF but reduced GLS while in septic shock [1,2,3,4,5]. It showed a discrete group of septic patients in whom there was normal 2D LVEF, but a decrease in GLS. It also showed that although the number of scans able to permit retrospective GLS calculation was low, that this is due to an easily remedied factor at our control. The image optimisation to enable GLS calculation is subtly different than the requirements of standard 2D EF. Without knowing that GLS was to be performed, the staff had not acquired images compatible for GLS. Staff training has already been carried out to correct this and the majority of equipment on site now supports 3D and GLS.

The lead investigator is an experienced echocardiographer with accreditation by the BSE and has undertaken courses on 3D and GLS. Co-investigators are experienced clinical staff

with in depth knowledge of the intensive care patient and a focus in cardiology and/or echo. The cardiology and critical care departments are well resourced to support the study throughout its course.

## 6.0 AIMS AND OBJECTIVES

### 6.1 **Primary Objective**

Can 3D LVEF, or GLS, provide an earlier indicator of LV failure in sepsis and septic shock compared to 2D LVEF?

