## 2.0 SYNOPSIS

Study Title	The assessment of left ventricular (LV) function in septic shock; comparison of ejection fraction measurement (both by two-dimensional and three- dimensional echocardiography), Global Longitudinal Strain, high sensitivity Troponin and NT proBNP. The assessment of left ventricular function in septic shock; comparison of ejection fraction measurement (both by two-dimensional and three-dimensional echocardiography), Global Longitudinal Strain, high sensitivity Troponin and Pro NT BNP
Short Title	GLASSheart
Internal ref. no.	PHT/2017/431
Problem statement	2D Ejection Fraction (EF) is not universally accurate in identifying LV systolic dysfunction in septic shock. The early identification of systolic dysfunction can assist clinicians in guiding medical therapy to optimise cardiac output and organ perfusion. Other methods of LV assessment such as cardiac magnetic resonance imaging (MRI) or Positron emission tomography (PET) are not routinely performed on this population due to cost, time and practical limitations. The use of 3D EF is currently not routinely recommended by British Society of Echocardiography (BSE) guidelines. This study aims to determine which type of echocardiographic modality identifies the most patients with cardiac dysfunction. In addition, we would like to assess the feasibility of non-invasive cardiac output measurement in the critically unwell patient. Biomarkers commonly used to assess non-septic cardiomyopathies (i.e. NT-proBNP and high sensitivity troponins) will be measured to identify their potential relationship with septic cardiomyopathies. Additionally, individuals who have persistent impaired Global Longitudinal Strain (GLS) are at risk of long-term myocardial dysfunction despite apparent clinical recovery. The study aims to

	identify individuals who would benefit from further cardiology follow up.			
Research question / hypothesis	
 
To identify a possible association between echo assessment with GLS, 2D EF and 3D EF and biomarkers which are conventionally used in myocardial dysfunction.
 
To identify if sequential echocardiographic scans assessing GLS, 2D EF and 3D EF are suitable to monitor progression of cardiac dysfunction following an episode of critical illness.
 
Is GLS a suitable early predictor of cardiac dysfunction (as currently defined by reduced EF) both in the short and longer term in comparison to traditional EF measurements.
 
			

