### 4.0 BACKGROUND AND RATIONALE

#### Epidemiology

Sepsis-induced cardiomyopathy occurs in up to 14% of patients with sepsis, resulting in myocardial dysfunction [1]. Transthoracic echocardiographic (TTE) assessment of left ventricular ejection fraction (LVEF) is typically used to define sepsis-induced cardiomyopathy. Recent meta-analysis demonstrates that low LVEF was not associated with mortality in septic patients [2,3].

Critically ill patients with sepsis were statistically significantly more likely to have low Global Longitudinal Strain (GLS) compared with reduced LVEF [4,5]. However these studies have been conducted with a small sample size. In addition, there has been no previous exploration of the value of biomarkers and the correlation with LV function.

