## 14.2 Analysis of Endpoints

Using the assistance of University of Portsmouth statistician, a recommendation of a sample size of 30 in each arm (90 in total), for the test of a single contrast at 0.05 significant level in a one way repeated measures analysis of variance with 3 levels will have 90% power to detect an effect size of 0.15.

In addition to 20% inflation of minimum sample size at baseline data collection due to likelihood of poor echo imaging, the number of expected participants decreases over the subsequent 3 data collection points to account for expected mortality in this cohort. All withdrawal will be logged in a case report form. Furthermore the feasibility of 3D imaging is a secondary outcome of this study.

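### The primary question is which modality turns abnormal earlier, but the primary analysis and the 90% power are for an ANOVA on means, so no power was calculated for timing

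*Protocol*

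**What the plan says.** Protocol 6.1 sets the primary objective as "Can 3D LVEF, or GLS, provide an earlier indicator of LV failure in sepsis and septic shock compared to 2D LVEF", and 7.2 repeats it as the primary outcome measure. Scans are planned at 24 h, 72 h, 30 days and 90 days (11.1).

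The analysis given for this objective in 14.1 is a univariate one-way repeated measures ANOVA. Section 9.0 bases the sample size on a repeated measures ANOVA with three arms and four time points, 5% significance, 90% power and an effect size of 0.15, giving 89 and, after 20% inflation, 108. Section 14.2 words it as a single contrast with three levels and a total of 90, which "will have 90% power to detect an effect size of 0.15".

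The Epidemiology part of section 4.0 states "Sepsis-induced cardiomyopathy occurs in up to 14% of patients with sepsis, resulting in myocardial dysfunction" and adds that "left ventricular ejection fraction (LVEF) is typically used to define sepsis-induced cardiomyopathy". The synopsis also gives an aim of another kind: "This study aims to determine which type of echocardiographic modality identifies the most patients with cardiac dysfunction".

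**The concern.** An earlier indicator is one that becomes abnormal at a visit before the comparator does. An ANOVA across modalities or visits tests whether mean readings differ. A difference in means does not show which reading crossed its threshold first in any patient. The 90% power therefore belongs to a comparison that does not answer the primary question. The protocol itself fixes the objective, the analysis and the power, so the mismatch is not a detail left to a statistical analysis plan.

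The synopsis aim of finding the modality that identifies the most patients adds to the risk. A higher detection rate at the first scan, or a difference in means, could be reported as an earlier signal, with the stated power seeming to stand behind it.

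**Working it through.** **1. What the 90% refers to.** Inputs from 9.0 and 14.2: effect size 0.15, 5% significance, 90% power. The metric of the effect size and the within-patient correlation (rho) are not given. Taking 0.15 as Cohen's f in a one-group repeated measures ANOVA with m measurements, the noncentrality is f² × n × m / (1 − rho).

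| m | rho (assumption) | n for 90% power |
|---|---|---|
| 4 | 0.45 | 88 |
| 4 | 0.50 | 81 |
| 3 | 0.50 | 96 |

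The base figure of 89 or 90 is thus close to an ANOVA on means under a plausible but unstated correlation; it is not reproduced exactly. The inflation step gives 89 × 1.2 = 106.8 and 90 × 1.2 = 108. No time to abnormality, order of onset or timing effect enters at any point.

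**2. Who can show a lead over an observed 2D fall.** With fixed visits, the paths are:

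- 2D EF normal at scan 1 and reduced later: a lead by GLS or 3D EF can be observed.
- 2D EF reduced at scan 1, new modality normal: an observed 2D-first order.
- Both abnormal for the first time at the same scan, including scan 1: a tie.
- New modality abnormal, 2D EF never reduced: the 2D time is censored, and no 2D fall is observed.
- Death before a 2D fall: no 2D fall is observed.
- Neither abnormal: no order.

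A lead over an observed fall arises only on the first path.

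**3. How many.** Assume that the up-to-14% figure, given for sepsis in general, applies to this ICU cohort and counts all EF-defined cases over follow-up. Then 0.14 × 89 = 12.5 and 0.14 × 108 = 15.1, so about 12 to 15 patients before removing those already reduced at scan 1. At 30% (assumption), 0.30 × 89 = 26.7 and 0.30 × 108 = 32.4, so about 27 to 32. Under the same assumption, patients with 2D EF already reduced at scan 1 are among these EF-defined cases, so counting them as 2D-first or tied does not raise the ceiling.

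**4. What such numbers can support.** The sign test is chosen here, since the protocol names no timing test. It is exact, two-sided at 5%, on patients with an order (new modality first or 2D first). Power = P(X ≥ r), with X binomial(n, p), r the critical count and p the true share with the new modality first.

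- n = 12, r = 10 (actual level 0.039). At p = 0.75: 66 × 0.75¹⁰ × 0.25² + 12 × 0.75¹¹ × 0.25 + 0.75¹² = 0.39. Power is 0.56 at p = 0.80 and reaches 90% at p of about 0.90.
- n = 15, r = 12 (actual level 0.035). At p = 0.75: 455 × 0.75¹² × 0.25³ + 105 × 0.75¹³ × 0.25² + 15 × 0.75¹⁴ × 0.25 + 0.75¹⁵ = 0.46. Power is 0.65 at p = 0.80 and reaches 90% at p of about 0.88.

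Because the test is discrete, 13 and 14 patients do slightly worse (0.33 and 0.28 at p = 0.75; 90% needs a share of about 0.91 and 0.92). At p = 0.80, 90% power needs 28 such patients, and 28 / 0.14 = 200 enrolled.

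**The case against.** **Scoring may be left to the analysis plan.** Rules for ties, censoring and death commonly are, and that stands: their absence is not the point here. The primary question and the analysis attached to it are both in the protocol, and they do not match.

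**A reader might infer that only patients with normal 2D EF at scan 1 and a later fall can be scored at all.** The documents do not support that. Reduced 2D EF with normal GLS or 3D EF at scan 1 is an observed order, with 2D first. Leaving such patients out would select on the comparator being late and tilt the result towards the new modality. LV failure is also not tied to a 2D fall throughout. Section 4.0 counts reduced GLS or EF as evidence of early dysfunction, and the preliminary work in 5.0 points to patients with normal 2D LVEF and low GLS. On that reading, patients outside the 14% also carry information.

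**A reader might take 12 to 15 as the protocol's own ceiling.** It is not. The 14% is an upper figure for sepsis in general, with no rate given for ICU sepsis or septic shock and no statement of whether it is prevalence at one scan or incidence over time. If it is early prevalence, later falls would come on top.

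**A reader might conclude that the study fails its stated 90% for timing.** No power was ever stated for timing, and the sign test and the 75% share are assumptions made here. With a true share of 90%, power is 0.89 at 12 patients and 0.94 at 15.

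**Conclusion.** The concern holds as a mismatch between question and analysis. The primary objective and outcome concern timing, the powered analysis concerns means, and the 90% does not carry over. This conclusion needs no prevalence figure.

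Its size does rest on assumptions: the 14% or 30% rate in this cohort, LV failure read as an observed 2D EF reduction, and a sign test. On the 14% assumption a lead must be nearly uniform before the study could show it with 90% power. At 30% there is more room, but if half of those patients were already reduced at scan 1 (assumption), 13 to 16 would remain. The documents support neither a firm ceiling on the number of scorable patients nor the claim that 90% power for timing is impossible.

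**What to change.** Amend 6.1, 7.2 and 14.2 as follows.

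- **(a) Detection.** Compare paired detection between modalities at the first scan in all patients with readable images, and call the result detection, not earliness.
- **(b) Timing.** Classify every patient by the first visit at which each modality is abnormal, and report each class with an exact confidence interval, without restriction to patients with normal 2D EF at scan 1. The classes are:
  - new modality first;
  - 2D first, including reduced 2D EF with normal GLS or 3D EF at scan 1;
  - tied, including all abnormal at scan 1;
  - new modality abnormal with 2D EF never reduced, reported separately;
  - neither abnormal;
  - death before a 2D fall.
- **(c) Power.** State that the 90% refers to the ANOVA only and that the timing comparison is descriptive.

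The cost is protocol wording, with no added scans or patients. The downside is that the stated power no longer covers the timing claim.

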#### 6.2 Secondary Objectives

- To explore any practical barriers to using GLS and three-dimensional echo methods by cardiac physiologists
- Is three dimensional EF feasible in the ICU population?
- To investigate whether there is an association between major adverse cardiac events at 12 months post sepsis or septic shock and any abnormal echocardiography results at any time point
- To investigate whether there is an association between major adverse cardiac events at 12 months post sepsis or septic shock and any abnormal biomarker results at any time point
- To compare 2D and 3D echocardiographic measurements with GLS to determine whether currently used definition of abnormality in GLS is appropriate.
- To compare 2D and 3D echocardiography measurements with GLS to identify if a range of abnormal GLS could be mapped to ranges of abnormal echocardiography results
- To compare troponin and BNP results with GLS to identify if a range of abnormal GLS could be mapped to ranges of abnormal biomarker results
- Can troponin or pro NT BNP measurements in combination with 3D LVEF, 2D LVEF or GLS provide an earlier indicator of LV failure in sepsis or septic shock

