## 7.0 STUDY DESIGN

## 7.1 Summary of Study Design

A prospective, cohort study based at a single centre (Queen Alexandra Hospital, Portsmouth). There is no randomization involved in this study. There is no blinding in this study. There will be a single operator for performing the scans due to the level of

Version 1.0 IRAS 247448

professional training and accreditation required to perform a GLS scan. Expected patient participation is 365 days (+/-7) or until mortality whichever occurs first.

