Laboratory assessments during admission for illness will include basic biochemistry and haematology. Biomarker assessments will have to be requested with prior agreement with the research laboratory based at QAH. The total volume of blood to be drawn for biomarker assessments will not exceed 10mls and will be divided into an EDTA (ethylenediaminetetraacetic acid) and SST (serum separating tube) bottle. The total volume to be drawn over the study for biomarkers and basic laboratory studies will not exceed 90mls.

Once participants have been discharged from critical care, they will be offered follow-up appointments at 30 days and 90 days from point of admission. If they remain within the hospital at 30 and 90 days, then assessment can be done whilst they are an inpatient.

MACE evaluation recorded at 12 months via notes review and/or telephone call to participant by heart failure nurses specialist to identify any out of area hospital admissions/interactions that are recorded as major adverse cardiovascular events such as: MI, stroke, hospitalization because of HF; and revascularization, including percutaneous coronary intervention, and coronary artery bypass graft

Some participants may be lost to follow-up or withdrawn from the study. This is detailed in section 10.5.

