## **11.0 INTERVENTIONS**

#### 11.1 Description of tests:

#### Echocardiography

Echocardiography is a non-invasive bedside ultrasound test which, in this study, will take approximately 15minutes and has no radiation risk. This will be performed at 24hrs, 72hrs, 30 days (+/-5) and 90 days (+/-5). A standard operating procedure exists for performing echocardiogram. Additional information is provided in a PIS for participants. In accordance with local practice, PPE equipment is worn for this test. ECG electrodes and ultrasound gel can be a potential risk to the patient with regards to dermatological reaction/sensitivity, however both are hypoallergenic substances. If a patient is observed to have any reaction to these consumables alternatives will be sourced or patient will be excluded from study.

There are no drugs used in this study. There are no placebos or alternative treatments.

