## NT pro-BNP

The N-Terminal pro-B-type Natriuretic Peptide (NT pro-BNP) blood test will be performed on all participants on admission, day 30 and day 90. This is a validated and prognostic test for heart failure and it is of value in other forms of myocardial dysfunction. Results will be recorded in the CRF.

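### 12-month MACE is related to an abnormal result at any visit up to day 90, so exposure can follow the event and early death cuts short both

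*Protocol*

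**What the plan says.** Section 6.2 (third and fourth bullets), section 7.2 (outcomes 3 and 4) and the synopsis carry the same two objectives. The first relates "major adverse cardiac events at 12 months post sepsis or septic shock and any abnormal echocardiography results at any time point". The second relates "major adverse cardiac events at 12 months post sepsis or septic shock and any abnormal biomarker results at any time point".

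- **Exposure visits.** Section 11.1 places echo at 24 h, 72 h, day 30 and day 90, the last two within 5 days either way. NT-proBNP is taken "on all participants on admission, day 30 and day 90", and troponin at the same visits. The synopsis endpoint list also shows 72 h for both biomarkers; the schedule in section 10.0 does not.
- **Outcome.** Section 10.3 evaluates MACE once, 12 months after inclusion, by notes review and/or telephone. It describes "major adverse cardiovascular events such as: MI, stroke, hospitalization because of HF; and revascularization, including percutaneous coronary intervention, and coronary artery bypass graft". Death is not among the listed components.
- **Follow-up.** Section 7.1: "Expected patient participation is 365 days (+/-7) or until mortality whichever occurs first". Sections 14.1 and 14.2 expect mortality to reduce numbers at each later visit, without giving a rate.
- **Analysis.** The only method named is repeated-measures ANOVA for the primary objective (14.1). None is named for the MACE association.

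**The concern.** An association with a 12-month outcome can be interpreted when exposure is known before the outcome is counted. Here exposure may be classified as late as day 90, while events count from the start. Two problems follow if the wording is applied literally.

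1. **Reverse timing.** A patient with an infarction on day 20 and an abnormal scan on day 30 or 90 counts as exposed with an event, although the event came first and may have caused the abnormality.
2. **Death-truncated opportunity.** A patient who dies on day 5 has had at most two scans and one biomarker sample, and almost no time for a MACE. A one-year survivor has had four scans, three samples and a full year. Survival acts on both sides of the comparison.

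The study aims to identify patients who would benefit from cardiology follow-up (synopsis). These two objectives are its stated link from test results to 12-month cardiac events, so a distorted estimate here would bear on that aim.

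**Working it through.** The protocol gives no figure for these objectives, so there is none to reproduce. The check asks what a literal ever/never comparison shows when abnormality and MACE are unrelated.

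**Step 1. Opportunity, by hand.** Let p be the chance of abnormality per scan, scans independent. Let D be the share dying between the second scan and day 30, assumed without MACE, and S = 1 − D the share surviving with all four scans. The chance of being ever abnormal after k scans is E_k = 1 − (1 − p)^k. The MACE risk in survivors cancels:

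RR = [S·E4 / (S·E4 + D·E2)] ÷ [S(1 − E4) / (S(1 − E4) + D(1 − E2))]

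Take p = 0.14, the upper figure for septic cardiomyopathy in section 4.0, and D = 0.30 (assumed).
- E2 = 1 − 0.86² = 0.2604; E4 = 1 − 0.86⁴ = 0.4530.
- Ever abnormal: survivors 0.70 × 0.4530 = 0.3171; dead 0.30 × 0.2604 = 0.0781; total 0.3952.
- Never abnormal: survivors 0.3829; dead 0.2219; total 0.6048.
- RR = (0.3171/0.3952) ÷ (0.3829/0.6048) = 0.802 ÷ 0.633 = 1.27.

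For biomarkers, with one sample against three and the same p and D: E1 = 0.14, E3 = 1 − 0.86³ = 0.3639, and RR = (0.2548/0.2968) ÷ (0.4452/0.7032) = 0.858 ÷ 0.633 = 1.36. With D = 0, RR = 1. Differential survival therefore produces the excess. Correlated scans shrink it.

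**Step 2. Simulation without a true association.** All inputs are assumed: 35% abnormal at every scan, within-patient correlation 0.3 to 0.6, 15% one-year MACE risk if alive, 30% to 67% mortality by day 90, 80% of those deaths by day 30, and a further 10% from day 90 to 365.

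| Setting | Odds ratio, ever abnormal |
|---|---|
| Constant 35%, deaths coded MACE-free | 1.19–1.73 |
| Same, 12-month survivors only | 1.00–1.01 |
| 12-month survivors only, half of post-MACE scans turn abnormal | 1.25–1.31 |
| Abnormality recovers (50%, 40%, 15%, 10%), deaths MACE-free | 1.03–1.17 |
| Recovery, and first-scan abnormality raises the death hazard | 0.79–0.97 |
| Landmark at day 4 or day 90, death unrelated to abnormality | 0.97–1.03 |

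**Step 3. A wider grid.** Prevalence 14%, 30% or 50%, correlation 0, 0.5 or 0.8, MACE 10% or 20% per year, deaths coded MACE-free. Zero mortality gave RR 1.00–1.01. With 30%, 40% and 67% dead at 12 months, RR was 1.06–1.70, 1.10–2.01 and 1.18–2.72. At correlation 0.5 to 0.8 the whole range was 1.06–1.48. About 27% to 36% of MACE fell before day 90, which is the share open to reverse timing.

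**Step 4. False positives.** In that grid, a 5% chi-square test with 108 patients rejected in 0.5% to 11.8% of trials, mostly 4% to 8%. Under the Step 2 inputs only about 6 to 11 MACE are expected among 108 patients.

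**The case against.** The strongest reply is that the protocol states an objective and not an analysis. "Any time point" can be read as testing each visit separately, and a landmark analysis in a statistical analysis plan that is not at hand could serve the same sentence. That stands in part: no ever/never table is prescribed. But the exposure and outcome windows are written into the objectives, and a sound analysis would have to narrow "any time point" and restrict which events count. That belongs in the wording.

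It is also fair that coding deaths as MACE-free is an assumption: among 12-month survivors the opportunity effect disappears. Reverse timing does not.

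A reader might infer four stronger things that the documents do not support.
- **Immortal-time bias.** That label does not fit a fixed 12-month table. It fits a naive time-to-event analysis in which scanning stops at MACE, and the bias then runs the other way (RR 0.62–0.95 in the wider grid).
- **Always away from the null.** The direction reverses if early abnormality recovers and predicts death.
- **Death ignored.** ICU, in-hospital and 30 or 90 day mortality are separate endpoints in the synopsis, and the MACE list is introduced as examples. What is missing is the link between death and this association.
- **Two-thirds mortality expected.** The one-third survival in section 4.0 comes from one background study, with no time horizon given. It is not a planning rate for this cohort.

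**Conclusion.** The point holds as a badly fixed definition. Exposure runs to day 90 inside an outcome window that opens at sepsis, so a literal reading lets results follow the events they are related to and ties both to survival. Size and sign depend on mortality, recovery of abnormality, whether abnormality predicts death, and how deaths are coded, none of which the protocol settles. With no true association, the odds ratio is roughly 1.2 to 1.7 under constant 35% prevalence with deaths coded MACE-free, and about 0.8 to 1.0 if early abnormality recovers and raises mortality. All of these inputs are assumptions.

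The harm is a biased estimate more than a false claim of significance: with 108 patients the false-positive rate moves little. The objectives are secondary, with few expected events and no decision rule attached. It should be fixed, but it does not threaten the primary objective.

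**What to change.** Reword the two objectives in section 6.2, section 7.2 and the synopsis.

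- Define exposure as the result at, or up to, a stated visit: for example the first scan or sample, with landmarks at day 30 and day 90.
- Count only MACE after that visit, in patients alive and MACE-free at it. A Cox model with the abnormal result as a time-updated covariate is an alternative.
- Treat death without MACE as a competing event, with cause-specific hazards and cumulative incidence, and report death alongside MACE. A landmark alone is not enough if abnormality predicts death, because later deaths would still sit among the MACE-free.
- State whether the MACE list in section 10.3 is complete and whether it includes cardiovascular death.
- Record the date of each MACE and of death on the case report form at the 12-month evaluation.

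The cost is wording, analysis code and two date fields that notes review should be able to supply. The downside is fewer patients and events at the later landmarks, so those estimates will be imprecise and are best presented with confidence intervals as exploratory.
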